5.2.2. Secondary Endpoint(s)

- 1. RD risk subjects versus no-risk subjects will be compared in terms of:
 - Incidence of AE's and actions taken.
 - Healthcare resource utilization (including hospital length of stay, 30 days readmission rate and primary diagnosis upon readmission).
 - Subject mortality at 30 days.
- 2. The predictive value (sensitivity, specificity, etc.) of etCO2, RR, SpO2, and IPI will be correlated with the occurrence of RD and ORADE.
- 3. Cost associated with events and actions taken will be estimated retrospectively using standard cost data from different countries.

6. Study Design

PRODIGY is a prospective, post-market interventional, multi-center, international cohort study.

A derivation cohort will be used to derive the risk assessment tool. An internal validation cohort will be used for evaluating the prognostic value of the score for the prediction of RD. Capnography and pulse oximetry monitoring device data will be collected as well as clinical data related to respiratory depression. Subjects will be monitored per standard of care. Enrollment at any single site will be limited to 20% (approximately 330 subjects) to ensure poolability of the data across sites and reduce potential bias. Additional methods incorporated to minimize potential bias include the following:

- Systematic identification of potential subjects via screening
- Both surgical and non-surgical candidates are eligible as event rates may vary
- Adjudication of RD events by an independent review committee
- Diverse geographical site representation to account for difference in practice

Version 3.0, 29 Nov 2016

PRODIGY CIP

- Standard procedures and data collection requirements with a common electronic database for all sites
- Provision of product for all study subjects

Foreseeable factors that may compromise the outcome of the study include lack of enrollment or the lack of respiratory depression events.

Approximately 1650 subjects will be enrolled in up to 16 centers from the United States (US), Europe and Asia. Geographic distribution of sites is anticipated as 8 sites (50%) in the US, 5 (30%) in Europe and 3 (20%) in Asia. Additional locations may be added during the course of the study.

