6.1. Duration

At least 20 subjects per month are expected to be enrolled at each participating center. Each participating site may involve one or more wards, based on its distribution of subjects receiving opioid therapy.

The study is expected to last approximately 10-13 (10-12 months of enrollment plus 30 days from the last enrolled subject). Not all the participating centers will be active at the moment of enrollment start.

Each subject will be followed-up for a maximum period of 30 days.

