9.3. Subject Consent

The investigator or authorized designee must obtain written informed consent before any clinical study related activity takes place. Written informed consent must be obtained prior to administration of opioid medication. In addition, written informed consent must be obtained pre-operatively, if surgery is applicable.

Well in advance of the consent discussion, the subject should receive the EC/IRB approved Patient Information and Informed Consent Form. During the consent discussion, the investigator or his/her authorized designee must fully inform the patient of all aspects of the clinical study that are relevant to the patient's decision to participate in the clinical study. If a patient is illiterate, an impartial witness must be present during the entire informed consent discussion. All items addressed in the Patient Information and the Informed Consent Form must be explained. The language used shall be as non-technical as possible and must be understandable to the patient and the impartial witness, where applicable.

The patient must have ample time and opportunity to read and understand the Patient Information and the Informed Consent Form, to inquire about details of the clinical study, and to decide whether or not to participate in the clinical study. All questions about the clinical study should be answered to the satisfaction of the patient.

Neither the investigator, nor the investigation site staff shall coerce or unduly influence a patient to participate or to continue to participate in the clinical study. The informed consent process shall not waive or appear to waive the patient's rights.

When the patient decides to participate in the clinical study, the Informed Consent Form must be signed and personally dated by the patient and investigator or authorized designee. If applicable, the witness shall also sign and personally date the consent form to attest that the information in the Patient Information and Informed Consent Form was accurately explained and clearly understood by the subject, and that informed consent was freely given.

After all persons have signed and dated the Informed Consent Form, the investigator must provide the subject with a copy of the Patient Information and the Informed Consent Form.

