9.5. Enrollment

The point of enrollment is informed consent completed and inclusion/exclusion criteria are confirmed per the screening evaluation.

Data collected for enrolled subjects includes:

- Medical history (including surgical, apnea, substance use, and medical therapy such as oxygen use and opioid use)
- Demographic & Physical exam
- Vital signs
- Supplemental oxygen use
- Surgery information (post-surgical subjects only)

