9.6. Capnography Monitoring Period

Each subject will be clinically monitored through standard methods (as per clinical practice of the site). Additional continuous data from the Capnostream monitor will be collected for a maximum of 48 hours to identify potential indicators of respiratory depression.

Monitoring of capnography and pulse oximeter data with the Capnostream monitor will start after opioid therapy has been initiated for subjects that will receive their first opioid therapy dose while on the hospital ward. The monitoring period will start for subjects once they arrive on the ward, for those subjects where opioid therapy was initiated prior to arrival on the hospital ward.

Monitoring may be discontinued after a minimum of 4 hours from the last dose of opioid therapy received or if the subject is discharged from the hospital ward.

Monitoring duration may be determined in periods, as deemed clinically appropriate during opioid therapy. An example of monitoring split into three periods:

PRODIGY CIP

- Period 1: first 24 hours continuous monitoring after enrollment (mandatory).
- Period 2: 12 hours continuous monitoring (to be performed for guidance during the first night following Period 1, from 7pm to 7 am).
- Period 3: 12 hours continuous monitoring (to be performed for guidance during the second night following Period 1, from 7pm to 7 am).

The suggested monitoring setting for Periods 2 and 3 has been proposed to facilitate subject's motion during daytime, thus covering the nighttime period at higher risk of developing RD events⁶. The alarm feature of the monitoring device will be silenced and the screen information blinded. A periodic check during the monitoring period should be completed to ensure the etCO₂ filter line and SpO₂ sensor are appropriately fitted on the subject.

Apart from the capnographic monitoring, no other device or concomitant medications different from clinical practice may be used during PRODIGY Study.

The Monitoring eCRF will be completed to document:

- Care pathway (location/transfers within the hospital)
- Monitoring duration
- Vital signs
- Supplemental oxygen use
- Medications
- Product information

At the end of the monitoring period the subject will be treated according to the hospital clinical practice and remain in the study for a maximum period of 30 days from the start of opioid therapy.

9.7. 1-Month Follow Up

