A 1 Month Follow Up visit (performed by phone if subject has been discharged) will be performed at 30 days (± 10 days) from enrollment.

Complete the 1 Month Follow Up eCRF. In addition, complete the applicable eCRFs to collect information related to:

- Adverse Events, if applicable to understand if any occurrence such as ORADE occurrence or mortality.
- Healthcare resource utilization (including hospital length of stay, readmission rate and related primary diagnosis).

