9.8. Study Exit

The Study Exit eCRF will be used to document that the subject has exited from the study. The reason for study exit will be captured on the Study Exit eCRF.

In addition, if the visit does not follow the 1-Month Follow-Up Visit, complete the applicable eCRFs to collect information related to:

- Adverse Events, if applicable to understand if any occurrence such as ORADE occurrence or mortality.
- Healthcare resource utilization (including hospital length of stay, readmission rate and related primary diagnosis).

If the study exit was for any reason other than normal study completion, see section 9.12 for information related to subject withdrawal or discontinuation.

PRODIGY CIP

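### The ±10-day window lets the only planned post-discharge contact fall as early as day 20, so 30-day mortality and readmission may be incompletely ascertained

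*Protocol*

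**What the plan says.** **Endpoints.** Protocol 5.2.2 lists, within secondary endpoint 1, "Subject mortality at 30 days" and "30 days readmission rate and primary diagnosis upon readmission". SAP 7.10.2.1 keeps both and leaves further detail to a Health Economic Analysis Plan. No time origin is given for either.

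**Contact.** Protocol 9.7 sets one visit, by phone after discharge, which "will be performed at 30 days (± 10 days) from enrollment".

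**Collection after the contact.** Table 2 of the protocol marks adverse events and resource utilization at study exit as well. Protocol 9.8 narrows this: "if the visit does not follow the 1-Month Follow-Up Visit, complete the applicable eCRFs". When exit follows the 1-month visit, these items are not asked again. Protocol 9.1 ends adverse event reporting at exit.

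**Length of follow-up.** Protocol 6.1 states: "Each subject will be followed-up for a maximum period of 30 days". Protocol 9.6, like the Synopsis, has subjects "remain in the study for a maximum period of 30 days from the start of opioid therapy". Protocol 9.7 runs to day 40 and counts from enrollment.

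**Clocks.** Under Protocol 9.5, "The point of enrollment is informed consent completed and inclusion/exclusion criteria are confirmed". Under 9.3, consent must come before opioids, and "written informed consent must be obtained pre-operatively, if surgery is applicable". Enrollment and opioid start are therefore different origins.

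**The concern.** A 30-day outcome is complete only if status is known on or after day 30. A contact on any of days 20 to 29 satisfies the protocol, closes the subject's follow-up, and leaves the rest of the 30 days unseen. Protocol 9.12 makes a missed 1-month contact a deviation, but nothing marks an early one as giving an incomplete outcome.

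The analysis text does not deal with this. Protocol 13.4 compares categorical secondary variables with chi-square, Fisher or Cochran-Mantel-Haenszel tests, which need a known yes or no for each subject. SAP 7.1.3 uses data to the last collection point for dropouts and for short monitoring; it gives no rule for a subject who completes on time but before day 30.

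At stake are two named components of a secondary endpoint. Deaths and readmissions between an early contact and day 30 may go unrecorded, and the reported 30-day rates would then be too low by an unknown amount.

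**Working it through.** **The plan's own figures.** The documents state no figure for completeness of 30-day outcomes. The sample size is used here only for scale, and it reproduces: 10 events × 12 variables / 0.12 = 1,000 derivation subjects; 1,000 / (2/3) = 1,500; 1,500 × 1.10 = 1,650.

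**Window.** 30 − 10 = day 20 and 30 + 10 = day 40, counted from enrollment. A contact on day *d* < 30 leaves 30 − *d* days uncovered, so the maximum is 10 of 30 days (33%).

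**Share affected.** Every contact pattern below is an assumption.

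| Assumed contact days | Before day 30 | Mean days lost, all subjects | Share of 30-day horizon |
|---|---|---|---|
| All on day 30 or later | 0% | 0 | 0% |
| Centred on day 30, SD 2 | 40% | 0.78 | 2.6% |
| Centred on day 30, SD 5 | 46% | 1.83 | 6.1% |
| Uniform over days 20-40 | 48% | 2.62 | 8.7% |
| All on day 20 | 100% | 10 | 33% |

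The two centred rows are bell-shaped patterns cut to whole days 20 to 40.

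The uniform row counts whole days. Ten of the 21 permitted days come before day 30: 10/21 = 47.6%, or 714 of 1,500 (786 of 1,650). Mean loss is (1 + 2 + … + 10)/21 = 55/21 = 2.62 days, and 2.62/30 = 8.7%. Treating time as continuous gives 50% early with a mean shortfall of 5 days: 0.5 × 5/30 = 8.3%.

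**Readmission counted from discharge.** The origin is not stated, so this is a second assumption. With a stay of *L* days, a contact on day 30 covers 30 − *L* days after discharge. For *L* = 2 to 7 that is 28 down to 23 days. With uniform contacts, the share covering fewer than 30 days after discharge is (10 + *L*)/21: 12/21 = 57% for *L* = 2 and 17/21 = 81% for *L* = 7.

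**After the change.** With contacts limited to days 30 to 40, the share contacted before day 30 is 0% and no days are uncovered, on the enrollment clock.

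**The case against.** The visit is targeted at day 30 and the ±10 days is a tolerance. A reader might infer from the window that 30-day outcomes cannot be observed for many subjects. The documents do not support that. They give no contact-day distribution, and the early share could be anything from 0% to 100%. Events before the contact are captured, a contact from day 30 on covers the whole horizon, and an early contact loses at most its last 1 to 10 days. The percentages above are lost observation time under assumed patterns, not lost events.

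A reader might also infer that unseen events will be scored as non-events. Neither document says so. SAP 7.8 derives each subject's study exposure, Protocol 13.4 also plans Poisson or negative binomial rate models (with no exposure offset stated), and the Health Economic Analysis Plan, which was not available, may hold a rule. Any such rule would have to assume that contact timing is unrelated to risk, and no rule can recover events that were never collected.

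A third inference is that ascertainment will differ by RD status. That is conjecture: the monitor screen is blinded, RD is adjudicated by an independent committee, and callers would generally not know the adjudicated result. A link through length of stay is possible but not shown.

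Finally, events on days 31 to 40 are mostly not a problem. Protocol 11 collects all serious adverse events and 11.2 requires the event date, so late deaths and most readmissions can be cut at day 30. The exception is a planned hospitalization, which the note in 11.1 excludes from serious events.

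What stands is the gap before day 30.

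**Conclusion.** The point holds as a risk of incomplete ascertainment. A fully compliant contact can leave up to 10 of 30 days unobserved, and neither document plans anything to close the gap. Assuming a uniform spread over days 20 to 40, about 48-50% of contacts are early and about 8-9% of the horizon is unobserved; the limits are 0% and 33%. The true share, the number of missed events and any effect on the RD comparison cannot be derived from the documents.

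Separately, the follow-up statements disagree on both length and origin. The Synopsis also describes follow-up as approximately 30 days, which softens the 30-versus-40-day conflict but does not settle the origin.

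The primary endpoint rests on a monitoring period of at most 48 hours and is untouched, as is the sample size. The change is still worth making because it is cheap and the lost information cannot be regained later.

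**What to change.** 1. In Protocol 9.7, set the contact window to day 30 through day 40 (0/+10 days) from one stated time origin.
2. State in the protocol and SAP that only deaths and readmissions dated on or before day 30 count. Ask for the readmission date on the utilization form, since planned readmissions need not appear as adverse events.
3. State the origin for each endpoint. If readmission is counted from discharge, time the contact to cover 30 days after discharge, or redefine the endpoint from enrollment. On the discharge clock a stay of up to 10 days still fits a day-40 limit (30 + 10 = 40); a longer stay would not.
4. Reconcile the 30-day maximum in the Synopsis, Protocol 6.1 and Protocol 9.6 with the new window. Otherwise the change deepens the existing conflict.

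**Cost.** Protocol, SAP and eCRF wording. It remains one contact per subject, and the latest permitted day on the enrollment clock stays at 40. Some subjects exit up to 10 days later than they could now.

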9.8. Study Exit

The Study Exit eCRF will be used to document that the subject has exited from the study. The reason for study exit will be captured on the Study Exit eCRF.

In addition, if the visit does not follow the 1-Month Follow-Up Visit, complete the applicable eCRFs to collect information related to:

- Adverse Events, if applicable to understand if any occurrence such as ORADE occurrence or mortality.
- Healthcare resource utilization (including hospital length of stay, readmission rate and related primary diagnosis).

If the study exit was for any reason other than normal study completion, see section 9.12 for information related to subject withdrawal or discontinuation.

PRODIGY CIP

9.9. Assessment of Safety

Methods and timing for assessing, recording, and analyzing safety parameters, including adverse events are described in the Adverse Event section.

9.10. Recording Data

The investigator will clearly mark the clinical records to indicate that the subject is enrolled in this clinical study. Subject's medical record will be used as source documents. Worksheets could serve as source documentation in particular cases if a data field is not in the subject's medical record.

Capnostream device memory data will be the source for the number and duration of RD episodes. RD data reports will be derived from the device memory data. The reports are used for primary endpoint validation from the Clinical Event Committee.

The investigator must ensure accuracy, completeness and timeliness of the data reported in the eCRFs and in all other required reports. Data reported on the eCRFs which are derived from source documents, such as patient medical records, must be consistent with the source documents or the discrepancies need to be justified in a documented rationale, signed and dated by the (principal) investigator, to be filed in the subject file. All baseline and medical history data must be derived from source documents.

Only authorized persons can complete eCRFs. Training will be provided to site personnel on the use of data collection tools. CRFs shall be electronically signed by investigators (physician) or by authorized site staff as specified on the Delegated Tasks List. Final version of eCRFs will be provided to the investigation sites when the investigational site has been declared ready for the study.

It is expected that eCRF will be completed within 15 days from the performed visit or as soon as source documents are available, except for Serious Adverse Events that require immediate reporting (see Table 3) and for Protocol Deviation requiring pre-approval. A delayed completion of the eCRF will not be considered a Protocol Deviation.

Sponsor study personnel will review all collected data and create data queries for missing data that impacts data analysis. Queries will be sent to the investigator or appropriate support staff for resolution.

Data reported on the eCRFs that are derived from source documents must be consistent with the source documents. Where copies of the original source document as well as print outs of original electronic source documents are retained, these shall be signed and dated by a member of the investigation site team with a statement that it is a true reproduction of the original source document.

9.11. Deviation Handling

Deviations are instance(s) of failure to follow, intentionally or unintentionally, the requirements of the CIP. Intentional deviations are not permitted, except where necessary to protect the life or physical wellbeing of a subject in an emergency situation. All deviations must be documented and explained, regardless of the reason for the deviation. Deviations will be documented on the Protocol Deviation eCRF.

If circumstances permit, the principal investigator is required to obtain prior approval from Medtronic before initiating actions that are considered study deviations. Prior approval from EC/IRB or competent authority might also be needed if related to safety, well-being or integrity of scientific data. Prior approval is not always realistic in situations where unforeseen circumstances are beyond the investigator's control. However, also in these cases, the event is considered a deviation and shall be reported.

Version 3.0, 29 Nov 2016

PRODIGY CIP

COVMOPO0560

In any emergency situation the investigator shall exercise his/her judgment to safeguard the subject's interest. Such deviations from the Clinical Investigation Plan do not require the prior approval of Medtronic. The investigator shall report the deviation as soon as possible to Medtronic and the reviewing EC/IRB, if applicable. Medtronic will inform the regulatory authorities, if required.

Any deviation which may occur multiple times over the course of the study on the same subject because of a permanent change in the subject's condition is only reportable once for each subject.

Repetitive or serious investigator compliance issues may result in the need to initiate a corrective action plan, and in some cases freeze enrollment or ultimately terminate the investigator's participation in the clinical study.

Medtronic is responsible for reviewing deviations, assessing their significance, and identifying any additional corrective and/or preventive actions (e.g. amend the CIP, additional training, terminate the study, etc.).

9.12. Subject Withdrawal or Discontinuation

If a subject is withdrawn from the clinical study, the reason for withdrawal shall be recorded on the Study Exit eCRF and in the subject's medical record.

Possible reasons for withdrawn from the study are:

- Adverse Event;
- Subject is lost to follow-up;
- Subject withdrew consent;
- Investigator withdrew subject from the study for medical reasons;
- Investigator withdrew subject from the study due to inclusion/exclusion criteria not met (including opiod therapy not started).

If discontinuation is because of safety or lack of effectiveness, the subject shall be asked to be followed for collecting safety data outside the clinical study. A missed 1 Month Follow Up will be considered a Protocol Deviation and the reason should be documented on the Protocol Deviation eCRF.

Subjects will be considered lost-to-follow-up after three documented attempts of contact. The relative information will be documented in the medical record. In addition, complete a Study Exit eCRF.

Subjects withdrawn for reasons other than screen failure will not be replaced.

10. Risks and Benefits

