9.1. Schedule of Events

Data will be collected for Screening, Enrollment Visit, the Capnographic Monitoring Period, 1 month Follow Up Visit, and Study Exit. Additional data will be collected for Adverse Events, Device Deficiencies, and Protocol Deviations.

Data collection requirements are summarized in Table 2. The study site personnel must report all study specific Adverse Events and changes in status of these Adverse Events from time of enrollment until a subject exits the study.

Table 2. Data Collection Requirements

PRODIGY CIP

056-F275, Clinical Investigation Plan Template, Version 2.0

Data	Screening Evaluation	Enrollment	Capnography Monitoring	1 Month Follow up	Study Exit
Informed Consent	x				
Inclusion/Exclusion Criteria Evaluation	x				
Medical History		x			
Demographic & Physical Exam		x			
Vital Signs		x	x		
Supplemental Oxygen Use		x	x		
Surgery Information		x			
Care Pathway			x		
Monitoring Duration			x		
Medications		x	x		
Adverse Events		x	x	x	x
Device Memory Data			x		
Product Information			x		
Device Deficiencies			x		
Protocol Deviations	x	x	x	x	x
Healthcare Resource Utilization				x	x

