7.1.3 Analysis Sets

The following subject sets will be used for the analysis:

- The Full Analysis Set (FAS) includes all patients enrolled in the study those sign Patient Informed Consent, fulfill the inclusion and exclusion criteria. The FAS will be used for safety evaluation.
- The Modified Full Analysis Set (MFAS) includes all patients enrolled in the study those sign Patient Informed Consent, fulfill the inclusion and exclusion criteria, start opioid therapy and monitored in the ward. Patients will not be excluded from the MFAS population even if prematurely stops, intermittent use or does not start the monitoring. Patients with major protocol deviations will be excluded from the MFAS. The MFAS will be used to evaluate the primary analysis.
- The Potential Respiratory Depression Population Set (PRDPS) includes all patients in the MFAS and have at least one Episode-File and/or Clinical Event to be adjudicated. The PRDPS will be used for secondary endpoint#2.

The following table shows how each population set will be used for analyses:

Population set	Baseline assessment	Primary and Secondary Endpoints (#1,#3)	Secondary Endpoint#2	Adverse Events
FAS	√			√
MFAS	√	√		√
PRDPS	√		√	

For those patients who have less than the minimum monitoring, or who drop out of the study, the analyses will include all data up to the point of their last data collection.

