7.10.2.1 Secondary endpoint#1

The secondary objective#1 will be evaluated comparing subjects that will develop RD versus patients that will not develop RD in terms of:

- Incidence of AE and actions taken.
- Healthcare resource utilization (including hospital length of stay, 30 days readmission rate and primary diagnosis upon readmission).
- Subject mortality at 30 days.

This secondary objective will be explained in the Health Economic Analysis Plan (HEAP).

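### Deaths, SAEs and readmissions after a safety-related exit and before day 30 have no stated route into the RD versus no-RD comparison or the safety tables

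*Protocol*

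**What the plan says.** Protocol 9.12 lists an adverse event among the reasons for withdrawal, and also "Investigator withdrew subject from the study for medical reasons". For discontinuation because of safety or lack of effectiveness, it says that "the subject shall be asked to be followed for collecting safety data outside the clinical study". It adds that "Subjects withdrawn for reasons other than screen failure will not be replaced".

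Four other provisions fix what is recorded for such a subject:

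- Protocol 9.1 has sites report adverse events and changes in their status "from time of enrollment until a subject exits the study".
- Protocol 9.8 covers an early exit: "if the visit does not follow the 1-Month Follow-Up Visit, complete the applicable eCRFs to collect information related to" adverse events (including ORADE and death) and healthcare utilization (length of stay, readmission).
- SAP 7.1.3 keeps dropouts in the analysis, and for them "the analyses will include all data up to the point of their last data collection".
- Protocol 9.6 says that a subject whose monitoring has ended stays in the study for up to 30 days from the start of opioid therapy.

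The outcomes concerned are in secondary endpoint 1 (Protocol 5.2.2, SAP 7.10.2.1). The SAP compares subjects who develop RD with those who do not on adverse events, healthcare utilization including 30-day readmission, and "Subject mortality at 30 days". It defers the detail to a Health Economic Analysis Plan (HEAP), which is not among the documents. The adverse event and death tables are in SAP 7.11.

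**The concern.** The endpoint is defined at 30 days, but for one class of subject data collection may stop well before then. That class is not a random one: these subjects left because of an adverse event or a medical problem. If such exits are more frequent among RD subjects, the missing follow-up is informative, and a comparison that counts these subjects as event-free after exit would tend to understate the RD versus no-RD difference. Whatever the balance between the groups, deaths and SAEs after such an exit would also be absent from the safety tables. The monitor is blinded and non-therapeutic, so a decision to stop it gives no scientific reason to stop asking about vital status.

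**Working it through.** **Step 1. Follow one subject through the text.** Take an invented case: exit for an adverse event on day 1, death on day 6.

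- Protocol 9.1: adverse event reporting ended on day 1.
- Protocol 9.8: the exit forms completed on day 1 cannot contain a day-6 death, a later readmission or the full length of stay.
- Protocol 9.12: later safety follow-up is requested, but outside the study. No section says that it enters the database.
- SAP 7.1.3: the subject stays in the analysis with data to last collection, here day 1.
- SAP 7.4: the imputation method is left open, and nothing addresses unknown day-30 status.

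The same subject with a death before exit would be fully captured. The gap runs only from exit to day 30.

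**Step 2. Look for a figure in the plan.** The only attrition figure is in the sample size. It reproduces: 12 variables × 10 events = 120 events; 120 / 0.12 = 1000; 1000 / (2/3) = 1500; 1500 × 1.10 = 1650. The 10% pools withdrawals, dropouts and screening failures, so no safety-exit rate can be taken from it. The documents give no 30-day mortality or readmission rate either.

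**Step 3. Illustrate with assumed inputs.** From the plan: 1500 subjects and 12% RD, hence 180 RD and 1320 no-RD. The rest is assumed:

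- true 30-day mortality of 2%, 3% or 5% in RD and 1% in no-RD;
- safety exits (w) of 1% to 5% in RD and 0.25% to 1% in no-RD;
- post-exit mortality (m) of 10% to 30%;
- every post-exit death missed, and the subject counted as alive.

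In each group, observed mortality = true mortality − w × m. Hence observed difference = true difference − m × (w_RD − w_noRD).

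- Mild end: 0.10 × (1% − 0.25%) = 0.075 points lost.
- Severe end: 0.30 × (5% − 1%) = 1.2 points lost.

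| True mortality, RD vs no-RD | True difference | Observed, mild | Observed, severe |
|---|---|---|---|
| 2% vs 1% | 1.0 | 1.9 − 0.975 = 0.925 | 0.5 − 0.7 = −0.20 |
| 3% vs 1% | 2.0 | 2.9 − 0.975 = 1.925 | 1.5 − 0.7 = 0.80 |
| 5% vs 1% | 4.0 | 4.9 − 0.975 = 3.925 | 3.5 − 0.7 = 2.80 |

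Deaths missed overall:

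- Mild: 180 × 0.001 + 1320 × 0.00025 = 0.18 + 0.33 = 0.51.
- Severe: 180 × 0.015 + 1320 × 0.003 = 2.70 + 3.96 = 6.66.

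The true totals in the three rows are 16.8, 18.6 and 22.2 deaths, so the share missed runs from 2% (0.51 / 22.2) to 40% (6.66 / 16.8).

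The formula also shows what the direction depends on. With equal exit rates and equal post-exit mortality in the two groups, the mortality difference is unchanged and only the death count falls. With more exits in the no-RD group, the difference would grow.

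**The case against.** A reader might infer that the deaths and readmissions of the sickest RD subjects drop out of the comparison, or that moving a subject to intensive care ends participation. The documents do not support this.

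- Events up to exit are collected and the subject stays in the analysis set. Ending monitoring is not an exit (Protocol 9.6), and SAP 7.1.3 keeps subjects whose monitoring stops early.
- Protocol 9.12 does not name ICU transfer or intubation as a reason to withdraw. Section 9.6 records transfers, and Appendix A lists ICU transfer, ventilation and respiratory death as anticipated adverse events.
- The screen is blinded and the alarms are silenced, so RD seen only on the device cannot prompt a withdrawal. Asymptomatic RD without action is not an adverse event (Section 11). Some adverse event exits may be for skin irritation.
- The reference to lack of effectiveness suggests generic wording that may seldom apply.
- A missed 1-month follow-up is a protocol deviation, with no exemption for safety exits.
- The HEAP may deal with unknown day-30 status.
- With 5.4 and 13.2 expected deaths (3% vs 1%), the risk ratio of 3.0 has a 95% interval of about 1.1 to 8.1 (SE of log RR = √(1/5.4 − 1/180 + 1/13.2 − 1/1320) = 0.50). One or two lost deaths lie within that noise.

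Most of this stands and limits the point. Three parts do not close the gap. A deviation record gives a reason but not an outcome, and 9.8 itself provides for exits with no 1-month visit. The HEAP can specify how missing status is analysed, but it cannot supply data that the protocol does not collect, and the death and adverse event tables belong to the SAP. Wide sampling error does not excuse an avoidable systematic loss when each missed RD death moves that group's mortality by 1/180 = 0.56 points.

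**Conclusion.** The point holds as a gap in data collection, not as a demonstrated bias. For subjects who leave for safety, events between exit and day 30 have no stated route into secondary endpoint 1, the costs that draw on it, or the death and adverse event tables. The risk score and the primary RD endpoint, which come from the monitoring period, are not affected.

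It is plausible that such exits are more common in RD subjects. The adverse events collected are respiratory events, device effects and SAEs, and any respiratory ORADE is itself listed among the data suggestive of RD (Protocol 5.2.1). That overlap exists only for clinically apparent events, and no withdrawal rate is given. It would therefore go too far to read the plan as known to bias the comparison toward no difference. Under the assumed ranges the mortality difference loses 0.075 to 1.2 points, and the result depends wholly on exit rates and post-exit mortality that the documents do not state. No figure was derived for readmission or length of stay. The change is worth making because it is cheap and removes a potentially informative loss.

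**What to change.** In Protocol 9.12, replace the clause that places safety follow-up outside the study. Subjects discontinued for an adverse event or medical reasons would remain in data collection through the existing 1-month follow-up: vital status, AEs and SAEs, readmission and utilization. Collection would end only on withdrawal of consent or loss to follow-up. This brings 9.12 into line with 9.6. It concerns data collection only and changes no clinical rule.

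In SAP 7.10.2.1 or the HEAP:

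- count these subjects to day 30;
- report study exits by RD status and reason;
- add a best-case and worst-case sensitivity analysis for unknown day-30 status.

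The cost is one protocol paragraph, a few lines in the analysis plan and a few more phone contacts. The 1-month visit and its eCRF already exist.
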